2.5 Statistical analysis, confidentiality plan

In terms of statistical analysis, SPSS 23.0 statistical software is used to establish a database and perform statistical processing. Descriptive statistical analysis, qualitative indicators are described as percentages, and quantitative indicators are described as mean \pm standard deviation. The data is subjected to normality testing and corresponding testing methods are adopted based on whether it follows a normal distribution. Qualitative data comparison adopts chi square test. Quantitative data conforms to normal distribution, t-test is used for comparison between two groups, and nonparametric test is used for abnormal distribution and $P<0.05$ is considered statistically significant.

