2.2 Study Description

The aim of this study is to observe the therapeutic effect of Baduanjin on improving shoulder joints in MHD patients. A total of 60 maintenance hemodialysis patients will be included and randomized into an intervention group of 30 cases and a control group of 30 cases. The intervention group underwent a 30 minute Baduanjin exercise under the guidance of a professional doctor before the dialysis day, including a 5-minute warm-up exercise, a 20 minute Baduanjin exercise, and a 5-minute relaxation exercise. The intervention group practice Baduanjin three days a week, while the control group maintain routine treatment and daily activities. Measure the indicators of each group at baseline, months 6, 12, and 18. The evaluation of shoulder joint function is based on the shoulder Constant score (which includes three dimensions: pain, daily living activities, and active range of motion); The quality of life score is based on the SF-12 score, and the emotional score is based on the Anxiety and Depression Scale.

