2.4 Outcome Measures

Primary Outcome Measure:

1) Shoulder joint function score

Using the adjusted version of the CMS scoring scale, the total score is 75 points, including pain (15 points), daily living ability (ADL, 20 points), and joint range of motion (ROM, 40 points).

2) Shoulder joint internal rotation function

The patient takes a standing position and measures the distance between the fingers and vertebrae of the hemodialysis patient's fistulae and non fistulae hands, that is, the patient moves their thumb with the backhand as much as possible along the midline of the back, and uses a tape measure to measure the closest distance from the tip of their thumb to the spinous process of the 7th cervical vertebra. Relevant data is organized and recorded.

3) Muscle strength measurement

Grip strength can reflect the strength of the hand muscles, and a grip strength meter is used to measure the grip strength of the patient's hands separately. The patient takes a standing position, holds the handle with maximum force, and records the value when the number on the machine display screen no longer changes. Test three times, take the maximum value, and record the relevant results.

4) Area of biceps brachii muscle

Measure the thickness of the biceps brachii muscle in two groups of patients through skeletal muscle ultrasound examination.

Secondary Outcome Measures:

1) Changes in the Short Form-36 (SF-36) and European Quality of Life Five Dimension (EQ-5D-5L)

Changes from the Short Form-36 (SF-36) and European Quality of Life Five Dimension (EQ-5D-5L) scale at 0 months, 8 months, 12 months. The SF-12 score is used to evaluate an individual's health status and quality of life. The SF-12 score expressed as a number between 0 and 100, with higher numbers indicating better health. EQ-5D-5L evaluate quality of life from five aspects: action ability, self-care, daily activities, pain or discomfort, anxiety or depression. The score range generally ranges from less than 0 to 1, and the higher the score, the better the state; The VAS score range is 0-100, with

higher scores indicating better health status.

2) Changes in the Hospital Anxiety and Depression Scale (HADS)

Changes from HADS Index at 0 months, 8 months, 12 months. HADS consists of 14 items, of which 7 items assess depression and 7 items assess anxiety. The scores for anxiety and depression range from 0 to 21, with higher scores indicating more severe symptoms.

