2.6 Preservation and Confidentiality of Information

The researcher preserves all research data, including confirmation of all participants (able to effectively verify different record materials, such as hospital original records), all original informed consent forms with subject signatures, all case observation forms, detailed records of evaluation indicators, etc.

The results of this project may be published in medical journals, but we will keep the information of the subjects confidential in accordance with legal requirements. Unless required by relevant laws, the personal information of the subjects will not be disclosed. When necessary, research supervision and management departments, hospital ethics committees and their relevant personnel may access patient information in accordance with regulations.

3. Exit and Termination Criteria

- 1) Those who do not receive regular exercise guidance from doctors, which affects the accuracy and effectiveness of research;
- 2) Those who experience adverse events and are not suitable for further observation;
The doctor determines that it is not suitable to continue observing the patient;

- 3) The subject experiences certain serious complications or complications, death or loss of follow-up, and is deemed unsuitable for further observation by the doctor;
- 4) During the research process, participants experienced endpoint events such as cardiovascular and cerebrovascular events and death.

4 Ethical issues

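### The planned two-group test leaves the baseline measurement unused; ANCOVA on baseline would probably sharpen a 30-per-arm comparison at almost no cost

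*Combined protocol and SAP*

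**What the plan says.** Section 2.5 is the whole analysis plan. The test is chosen by a normality check: "The data is subjected to normality testing and corresponding testing methods are adopted based on whether it follows a normal distribution". For quantitative data, "t-test is used for comparison between two groups, and nonparametric test is used for abnormal distribution". Significance is set at 0.05, with sidedness not stated. No covariate, ANCOVA, regression or repeated-measures model appears anywhere in the document.

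Section 2.2 provides for a baseline measurement: "Measure the indicators of each group at baseline, months 6, 12, and 18". It also gives the size of the trial, with patients "randomized into an intervention group of 30 cases and a control group of 30 cases".

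Section 2.4 lists four primary outcomes: the 75-point shoulder score, the thumb-to-C7 distance, grip strength, and the biceps measured by ultrasound. None is defined as a change from baseline. Only the secondary quality-of-life and mood outcomes carry that label, for example "Changes from HADS Index at 0 months, 8 months, 12 months".

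**The concern.** A score or strength measured twice in the same patient is usually correlated. The part of the follow-up variance that baseline explains can be removed from the treatment comparison without extra patients. The test in section 2.5 does not do this. If it is applied to follow-up values, baseline is ignored. If it is applied to changes, baseline enters by subtraction, which fixes its coefficient at 1 instead of estimating it, and this adds noise when the correlation is below 0.5.

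What is at stake is precision, not bias. The document gives no sample-size calculation, and 30 per arm is small. Section 3 also foresees withdrawals, including "The subject experiences certain serious complications or complications, death or loss of follow-up", so fewer than 30 per arm may be analysed. Because the plan does not say whether follow-up values or changes are tested for the primary outcomes, the choice could also be made after the data are seen.

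**Working it through.** **Inputs from the document.** 30 per arm (section 2.2); significance level 0.05 (section 2.5); outcomes measured at baseline and follow-up (section 2.2).

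**Assumptions, because the document gives no figure.** Two-sided test; true effect d = 0.5 SD; equal SD at baseline and follow-up; correlation r between baseline and follow-up from 0.3 to 0.7, with r = 0 as the worst case. The total of 60 cannot be reproduced, since no effect size, SD, power or dropout is stated, so n = 30 per arm is taken as fixed.

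**Standard error of the group difference, in SD units.**
- t-test on follow-up values: √(2/n), 2n − 2 = 58 df. √(2/30) = 0.258.
- t-test on change: √(2/n × 2(1 − r)), 58 df. At r = 0.5 the factor 2(1 − r) is 1, so this equals the follow-up test; below 0.5 it is worse.
- ANCOVA: √(2/n × (1 − r²) × (1 + 1/(2n − 4))), 2n − 3 = 57 df. The last factor, 1 + 1/56 = 1.018, is the expected cost of estimating the slope. At r = 0.5: √(0.0667 × 0.75 × 1.018) = 0.226.

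**Power at d = 0.5 (noncentral t) and effect detectable with 80% power, 30 per arm.**

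| r | Follow-up t-test | Change t-test | ANCOVA |
|---|---|---|---|
| 0.3 | 47.8%; 0.74 SD | 36.3%; 0.87 SD | 50.7%; 0.71 SD |
| 0.5 | 47.8%; 0.74 SD | 47.8%; 0.74 SD | 58.7%; 0.64 SD |
| 0.7 | 47.8%; 0.74 SD | 69.1%; 0.57 SD | 75%; 0.53 SD |

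**Precision of ANCOVA against the follow-up t-test.** The variance ratios are 0.926, 0.763 and 0.519 at r = 0.3, 0.5 and 0.7. Their square roots, 0.962, 0.874 and 0.720, correspond to intervals about 4%, 13% and 28% narrower. The equivalent unadjusted trial has 30/0.926 = 32, 30/0.763 = 39 and 30/0.519 = 58 patients per arm.

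**Precision of ANCOVA against the change t-test.** The standard errors are 0.248 against 0.306, 0.226 against 0.258, and 0.186 against 0.200. The intervals are therefore about 19%, 13% and 7% narrower.

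**Downside.** At r = 0, ANCOVA power is 47.1% against 47.8%, with variance 1.8% higher. Break-even with the follow-up t-test is at r of about 0.13.

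**Attrition.** At an assumed 24 per arm analysed, power for follow-up / change / ANCOVA is 40% / 30% / 42% (r = 0.3), 40% / 40% / 49% (r = 0.5) and 40% / 59% / 65% (r = 0.7).

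**Bounded score.** A simulation capped scores at 75, with an assumed latent mean of 65, SD of 9 and shift of 0.5 SD. Power for follow-up / change / ANCOVA was 45% / 32% / 48%, 45% / 41% / 55% and 45% / 60% / 70% at the three correlations. The type I error of ANCOVA was 5.0%. The Mann-Whitney test, which is the plan's nonparametric branch, had about 44% power in the same setting.

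**The case against.** The strongest reply is that nothing in section 2.5 is wrong. The t-test is valid under randomisation, and the gain from adjustment rests on a correlation that the document does not give. At r = 0.2 power rises by less than 1 point (47.8% to 48.6%), and at 0.3 by about 3. Follow-up is months after baseline, so a low correlation at late visits cannot be excluded. This stands, and it is why the point is an improvement rather than an error.

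Second, section 2.5 does not say which quantity is tested. If it is the change, the gain from ANCOVA at r = 0.7 is about 6 points of power (69% to 75%), not 27. That also stands. At r = 0.3, however, the gain over change scores is larger, about 14 points (36% to 51%), so ANCOVA is the better choice whichever test was meant.

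Third, a strong ceiling shrinks the benefit. With an assumed latent mean of 70 on the capped score, Mann-Whitney has about 42% power against about 43%, 48% and 61% for ANCOVA. The advantage at r = 0.3 is then about 1 point. It is smaller but not reversed.

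Fourth, after promising baseline measurement of the indicators, section 2.2 describes only the shoulder score, the quality-of-life score and the mood scale. For thumb-to-C7 distance, grip strength and the biceps, baseline collection is implied rather than listed. This should be confirmed before the change is called free of new data.

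**Conclusion.** The concern holds. The plan provides for a baseline measurement and then specifies a comparison that does not use it as a covariate. For an assumed 0.5 SD effect with 30 per arm, adjustment would raise power from 48% to between 51% and 75% for r from 0.3 to 0.7, and would lower the effect detectable with 80% power from 0.74 SD to between 0.71 and 0.53 SD. The worst case is a loss of 0.7 points. The size of the benefit depends on r and on the assumed effect, neither of which is in the document. The direction does not depend on a precise r, because break-even is as low as about 0.13. The planned analysis remains valid, so this is a change the sponsor should make to gain precision, not one needed to rescue the trial.

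**What to change.** 1. Reconcile the visit months (6, 12 and 18 in section 2.2; 0, 8 and 12 for the secondary outcomes in section 2.4), name one primary visit, and confirm that all four primary outcomes are measured at baseline.

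2. In section 2.5, replace the rule for continuous outcomes with text such as: *Each continuous outcome at the primary visit is analysed by ANCOVA of the follow-up value on randomised group and the baseline value of the same measure. The adjusted group difference is reported with its 95% confidence interval. A rank-based test is a sensitivity analysis.*

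3. If several visits are modelled together, use a repeated-measures model with group, visit, group-by-visit, baseline and baseline-by-visit terms and an unstructured covariance.

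4. Thumb-to-C7 distance is taken on both the fistula and non-fistula hands, and for grip "a grip strength meter is used to measure the grip strength of the patient's hands separately". State which hand is the analysed outcome and adjust for that hand's baseline.

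The cost is a few lines of text, slightly more analysis work, and settling the visit schedule, which the plan needs in any case. No new data are required if the baseline measurements in section 2.2 cover all four primary outcomes. If baseline proves uninformative, under 1 point of power is lost.

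### Only two-group tests are planned for outcomes measured repeatedly over 18 months, so early leavers fall out of later comparisons, which can bias them; most of the available month-18 precision gain comes from baseline adjustment

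*Combined protocol and SAP*

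**What the plan says.** Section 2.2 has 60 patients "randomized into an intervention group of 30 cases and a control group of 30 cases". On timing it says: "Measure the indicators of each group at baseline, months 6, 12, and 18".

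Section 2.5 is the whole analysis plan. A normality test decides the method, qualitative data get a chi-square test, and for quantitative data "t-test is used for comparison between two groups, and nonparametric test is used for abnormal distribution". It names no visit, repeated-measures model, baseline covariate, analysis set or method for missing values.

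Section 3 foresees patients leaving. One criterion reads "The subject experiences certain serious complications or complications, death or loss of follow-up", with the doctor judging whether observation continues. Others cover adverse events, cardiovascular or cerebrovascular events, and not receiving regular exercise guidance. The section does not say whether patients who exit are still measured or analysed.

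Section 2.4 gives a different timetable for the secondary outcomes, for example "Changes from HADS Index at 0 months, 8 months, 12 months".

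**The concern.** A two-group test uses one number per patient. At month 18 it can include only patients measured then, and what was recorded at months 6 and 12 for those who left plays no part. That is harmless to validity if leaving is unrelated to shoulder function, or related in the same way in both arms. Section 3 gives reason to doubt both conditions. Several exits follow health events. The exercise-guidance exit can in practice act only in the exercise arm, because section 2.2 leaves controls on routine treatment and daily activities.

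If exercise patients who are doing poorly at month 6 leave more often, those who remain look better at month 18 and the comparison favours exercise with no true effect. Adding the baseline value to a single-visit comparison helps only in part, because it still discards everyone missing at that visit.

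**Working it through.** The documents state no effect size, SD, power or dropout rate, so there is no figure to reproduce. The results below are illustrations in SD units.

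**From the documents:** 30 per arm; visits at 0, 6, 12 and 18 months (2.2); two-group test; P<0.05 (2.5).

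**Assumed:** two-sided testing; loss *f* of 20% or 30% per arm, all after month 6; constant correlation r = 0.5 to 0.8 between visits, or correlation decaying as r to the power of the visit lag; normal data.

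**1. Bias with no true effect.** Let exercise-arm exits come at random from the lower half of month-6 scores, and control exits be random. The lower half has mean −0.798 SD. Removing a fraction *f* of the arm from it moves the remaining patients' month-6 mean to 0.798 × f/(1−f). A fraction r of that carries to month 18:

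bias = 0.798 × r × f/(1−f)

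False positives come from a simulation of 6,000 trials per row. The last two columns give the bias, from the same simulation, of a baseline-adjusted month-18 comparison and of an estimate that also uses month-6 values of all patients.

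| f | r | Bias, formula | False positives, t-test | Bias, baseline-adjusted | Bias, using month 6 |
|---|---|---|---|---|---|
| 20% | 0.5 | 0.10 | 6.2% | 0.05 | 0.00 |
| 20% | 0.6 | 0.12 | 6.7% | 0.04 | 0.00 |
| 20% | 0.7 | 0.14 | 7.2% | 0.04 | 0.00 |
| 20% | 0.8 | 0.16 | 8.3% | 0.03 | 0.00 |
| 30% | 0.5 | 0.17 | 8.2% | 0.09 | 0.00 |
| 30% | 0.6 | 0.20 | 8.9% | 0.08 | 0.00 |
| 30% | 0.7 | 0.24 | 11.0% | 0.07 | 0.00 |
| 30% | 0.8 | 0.27 | 13.5% | 0.06 | 0.01 |

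With decaying correlation, r² replaces r, because month 18 is two visits after month 6. At adjacent-visit correlation 0.7 and 20% loss, the bias is 0.798 × 0.49 × 0.25 = 0.10 SD, with about 6% false positives.

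**2. Precision at month 18.** Take random loss of 20% (24 per arm), r = 0.6 constant and a true effect of 0.5 SD.

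- t-test: variance 2/24 = 0.0833, SE 0.289.
- Baseline-adjusted: (2/24) × (1 − 0.6²) = 0.0533, SE 0.231.
- Mixed model: given baseline and month 6, the residual variance is 1 − 2(0.36)/1.6 = 0.55. The part carried by month 6 beyond baseline is 0.375² × 0.64 = 0.09, estimated from all 30 per arm. Variance = (2/24)(0.55) + (2/30)(0.09) = 0.0518, SE 0.228.

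Power from the noncentral t distribution is about 40%, 56% and 58%. With no loss, the last two are identical at 66%, against 48% for the t-test.

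With correlation decaying at 0.6 per visit, the baseline-to-month-18 correlation is 0.6³ = 0.216. The mixed-model variance is (2/24)(0.8704) + (2/30)(0.0829) = 0.0781, SE 0.279. Power is about 42%, against 40% for the t-test.

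**3. Averaging over visits.** In the constant-correlation setting with 20% loss, the mean of months 6, 12 and 18 has SE 0.166.

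| Effect at months 6, 12, 18 (SD) | Average | Power of the average |
|---|---|---|
| 0.5, 0.5, 0.5 | 0.50 | about 84% |
| 0.17, 0.33, 0.5 | 0.33 | about 51% |
| 0, 0, 0.5 | 0.17 | about 17% |

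The baseline-adjusted month-18 test has about 56% in all three cases.

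**The case against.** A reader might infer that a mixed model would roughly double the trial's power, from about 40% to about 84%. That sets a month-18 test against a three-visit average under an effect assumed equal at every visit. Like for like at month 18, the intermediate visits add about 2 points beyond baseline adjustment. The rest comes from changing the quantity estimated, and the documents do not say that the average is the question. If the effect builds gradually, the average has less power than the baseline-adjusted month-18 test. This objection stands.

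A reader might also infer that the trial's later comparisons will be biased. The documents do not support that. They give no loss rate, and no exit criterion in section 3 is defined by shoulder score. The scenario above makes exit depend on a recorded score, which is the case a mixed model handles. Exits caused by unrecorded decline, and deaths, are not repaired by it. What remains is that bias is possible and the plan has no defence against it.

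Third, visit-by-visit testing is an inference. Section 2.5 names no visit, and 2.4 words the secondary outcomes as changes, so a test of change from baseline may be meant. That would use the baseline, but it would still drop anyone absent at the visit analysed.

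Finally, months 6, 12 and 18 cannot be applied to every outcome, since 2.4 puts the quality-of-life and HADS measures at 0, 8 and 12 months. Two follow-ups are still repeated measurement, so the point survives in that form.

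**Conclusion.** The concern holds as a gap in section 2.5: repeated quantitative outcomes, foreseen exits, and no method that uses a leaver's earlier values. If exit is related to earlier scores and differs by arm, month-18 bias is about 0.1 to 0.27 SD with 6-14% false positives. These sizes rest on assumed loss of 20-30% and constant correlation of 0.5-0.8; at a given loss they shrink if correlation decays. Baseline adjustment alone leaves 0.03 to 0.09 SD.

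Precision is a lesser argument. The month-18 gain comes almost entirely from baseline adjustment and is small under decaying correlation. The point is worth acting on because the remedy uses data already planned, but it does not show that the trial will mislead.

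**What to change.** In section 2.5, make the main analysis of each repeatedly measured quantitative outcome a linear mixed model. It should use all available follow-up values from all randomised patients, with arm, visit, arm-by-visit and baseline as fixed effects and correlated errors within patient. Use each outcome's own visits, after reconciling the schedules in 2.2 and 2.4.

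Name one contrast in advance as the treatment effect, either month 18 or the visit average. The sponsor should choose by its question, knowing that the average loses power if the effect builds late. Report visit-specific differences with 95% CIs, and keep the simple tests as sensitivity analyses. State whether patients who exit are still measured and how deaths are handled.

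The cost is protocol wording and some analysis time; the model itself needs no new patients or visits. The downside is reliance on missing at random given the observed values. That is weaker than what visit-by-visit tests need, but it does not cover deaths or exits driven by unrecorded decline.

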2.1 Research Purpose

Main objective: To observe the effect of Baduanjin on the shoulder joint function of maintenance dialysis patients.

Secondary objective: To observe the effect of Baduanjin on the quality of life and emotions of MHD patients.

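### Secondary objective (quality of life and emotions): at least five scores at two follow-up visits, each judged at an unadjusted P<0.05, with no key score, key visit, hierarchy or exploratory label

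*Combined protocol and SAP*

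**What the plan says.** Section 2.1 separates this objective from the shoulder-function objective: "Secondary objective: To observe the effect of Baduanjin on the quality of life and emotions of MHD patients".

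Section 2.4 describes at least five scores under the secondary outcomes, with their ranges:

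- SF score, headed SF-36 but described as SF-12: "The SF-12 score expressed as a number between 0 and 100, with higher numbers indicating better health".
- EQ-5D-5L index: "The score range generally ranges from less than 0 to 1, and the higher the score, the better the state".
- EQ VAS, which has its own 0-100 range.
- HADS anxiety and HADS depression, seven items each: "The scores for anxiety and depression range from 0 to 21, with higher scores indicating more severe symptoms".

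Section 2.4 places the follow-up of these measures at months 8 and 12. Section 2.2 places follow-up at months 6, 12 and 18, and for this objective names only the SF-12 and an anxiety and depression scale.

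Section 2.5 is the whole analysis plan. For quantitative data it says "t-test is used for comparison between two groups, and nonparametric test is used for abnormal distribution and $P<0.05$ is considered statistically significant". It does not state whether tests are one- or two-sided, whether each visit is tested separately, or how the several scores combine into a conclusion on the objective.

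**The concern.** One objective is backed by several scores and several visits, and any one of the resulting comparisons can be called statistically significant at the full 0.05. Nothing fixed in advance says which score or visit would count. One score at one visit could therefore be presented as Baduanjin improving quality of life or mood, and the plan gives no way to tell this from chance.

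This set of outcomes is distinct from the four primary outcomes in 2.4. Naming a single primary outcome would leave the rule for these scores unchanged.

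**Working it through.** The documents state no family-wise error rate, so there is no figure of theirs to reproduce.

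**Inputs from the documents**
- 60 patients randomised, 30 per arm (2.2).
- Threshold 0.05 per comparison, no adjustment (2.5).
- Five scores at months 8 and 12 (2.4): 5 × 2 = 10 tests.
- Section 2.2 read alone: two scales, or three scores if HADS is split, at three visits: 2 × 3 = 6 to 3 × 3 = 9 tests.

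**Assumptions (not in the documents)**
- Two-sided tests, hence 0.025 in the direction of benefit.
- A separate test at each visit.
- Between-score correlation 0 to 0.7; between-visit correlation 0.5 to 0.7.

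**Step 1: reference values if all tests were independent**
- Either direction, 10 tests: 1 − 0.95^10 = 40.1%.
- Benefit only, 10 tests: 1 − 0.975^10 = 22.4%.
- Either direction, 5 tests: 1 − 0.95^5 = 22.6%.
- Benefit only, 5 tests: 1 − 0.975^5 = 11.9%.

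**Step 2: correlated tests**
Simulation of 20,000 null trials per setting: multivariate normal data, 30 per arm, two-sample t-tests at two-sided 0.05, correlation matrix equal to the Kronecker product of the score and visit correlations.

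| Setting | At least one P<0.05, either direction | At least one P<0.05 favouring Baduanjin |
|---|---|---|
| 5 scores, 1 visit | 15-22.5% (about 19% at score correlation 0.5) | about 8-12% (about 9% at 0.5) |
| 5 scores, 2 visits (2.4) | about 24-38% (29-31% at 0.5) | about 12-21% (15-16% at 0.5) |
| 2-3 scores, 3 visits (2.2 alone) | about 18-33% | about 9-18% |

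**Step 3: comparison with a single test**
A single two-sided test allows 5% in either direction and 2.5% for benefit. For five scores at two visits, 12/2.5 = 4.8 and 21/2.5 = 8.4, so a chance benefit is about five to eight times as likely as with one test. At one visit the either-direction rate is still at least 15/5 = 3 times the nominal level.

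**Step 4: check of the remedy**
Bonferroni over five scores at one visit (0.05/5 = 0.01 each) gives 3.4-4.9% over the same score correlations. When no score has a true effect, Holm makes at least one rejection exactly when Bonferroni does, so the same figures apply to Holm.

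**The case against.** **Stronger readings that the documents do not support**
- A reader might infer that a chance benefit is about 29-31% likely. That figure counts a significant difference in either direction. The benefit-only rate under the same assumptions is about 15-16%, and it cannot exceed 22.4% even with 10 independent tests.
- A reader might count up to 15 tests by taking five scores at three visits. That joins the score list of 2.4 to the schedule of 2.2. Neither section alone lists five scores at months 6, 12 and 18; 2.2 alone gives about 6 to 9 tests.
- A reader might infer a rule that one significant score establishes the objective. The plan contains no such rule, and 2.1 speaks only of observing the effect. The weakness is that nothing rules this use out.

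**The case for leaving the plan as it is**
- Testing at each visit is inferred. This stands as a caveat, but 2.5 offers only two-group tests, with no repeated-measures or summary analysis that would reduce the count. With one visit the inflation remains.
- Separate testing of the two HADS subscales is likely but not stated, since 2.4 also speaks of a HADS index. The count of five depends on it.
- Secondary outcomes in a 60-patient trial are often left unadjusted and read as supportive. That is a fair position, but the plan does not take it: these outcomes serve a stated objective and fall under the same significance rule as the primaries. Saying so is the first remedy below.
- One multiplicity statement in 2.5 could also cover the primary outcomes. True, provided it names these scores as well.

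**Conclusion.** The point holds. Section 2.5 gives an unadjusted P<0.05 to every comparison behind the secondary objective, with nothing to rank or limit them. For five scores at months 8 and 12, the chance of at least one false-positive difference is about 24-38% in either direction and about 12-21% in favour of Baduanjin. These ranges rest on two-sided tests, separate testing at each visit, no true effect and the assumed correlations.

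The exact rate cannot be fixed until the number of scores and visits is settled, but the conclusion does not depend on that. Five scores at one visit, or the fewer scales of 2.2 at three visits, also exceed the nominal level by a factor of at least three.

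The main conclusion on shoulder function is not affected. What is at stake is what may be claimed about quality of life and mood, so the change should be made but does not put the trial's main result in doubt.

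**What to change.** Add to section 2.5, in one of two forms:

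1. *Default.* Quality-of-life and HADS comparisons are exploratory. They are reported as between-arm differences with 95% confidence intervals, and no claim of effect rests on an individual P<0.05.
2. *If a claim on the secondary objective is wanted.* Restrict it to the five scores at month 12, the only follow-up visit common to 2.2 and 2.4. Test them with Holm at a family level of 0.05, and label all other visits exploratory.

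In either case, reconcile months 6, 12 and 18 (2.2) with months 8 and 12 (2.4), and SF-36 with SF-12 within 2.4. State which scores each instrument contributes, that tests are two-sided, and whether visits are tested separately. Without these the family is undefined.

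The cost is one or two sentences plus that reconciliation, with no new data, visits or patients. The downside is that fewer secondary results can be called significant under the first form, or slightly lower power per score under the second.

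### Four outcomes are labelled primary and tested at an unadjusted P<0.05 with no success rule; if any one may count, the false-positive risk at one visit is about 9–18.5% for assumed correlations of 0.9 down to 0.

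*Combined protocol and SAP*

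**What the plan says.** Under the heading "Primary Outcome Measure", section 2.4 numbers four outcomes.

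1. A shoulder function score: "Using the adjusted version of the CMS scoring scale, the total score is 75 points".
2. Internal rotation, measured as a thumb-to-vertebra distance for the "fistulae and non fistulae hands".
3. Grip strength: "a grip strength meter is used to measure the grip strength of the patient's hands separately".
4. A biceps brachii ultrasound measure, called an area in its heading and a thickness in its text.

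Section 2.5 compares the groups with a t-test or a nonparametric test according to normality, under one general threshold: "nonparametric test is used for abnormal distribution and $P<0.05$ is considered statistically significant".

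Three other places bear on the point. Section 2.1 makes shoulder joint function the main objective without naming an instrument. Section 2.2 adds that "The evaluation of shoulder joint function is based on the shoulder Constant score" and sets the schedule: "Measure the indicators of each group at baseline, months 6, 12, and 18". Section 2.4 gives a different set of times for the secondary outcomes only, for example "Changes from HADS Index at 0 months, 8 months, 12 months".

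Nowhere do the documents rank the four primaries, combine them, adjust for testing several, name a primary visit, or say whether one significant result is enough or all four are required.

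**The concern.** With four primaries of equal standing and a 5% threshold for each, a reader cannot tell in advance what result would make the trial positive. The report could present whichever of the four reached P<0.05 as success on a primary outcome. A borderline result on grip strength could be reported that way while the CMS, the measure closest to the main objective, showed no difference.

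The trial is meant to supply evidence for recommending an exercise method (section 1), so a positive result selected from four would be put to use. The problem lies with borderline and selected results. A very small P-value on the CMS would remain credible.

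**Working it through.** **Inputs from the documents.** Four primary outcomes (section 2.4); 0.05 per test, no adjustment (section 2.5); 60 patients, 30 per group (section 2.2). The sample size is stated without power, effect size or SD, so there is no planning figure to reproduce, and the point does not depend on one.

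**Assumptions, because the documents are silent.** Two-sided tests; one test per outcome at one visit; no true effect on any of the four; any one P<0.05 counts as success; a common correlation r between the four outcomes.

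**Step 1: limits.**
- Perfect correlation: the four tests act as one, giving 5%.
- Upper bound under any dependence: 4 × 0.05 = 20%.
- Independence: 1 − 0.95^4 = 1 − 0.8145 = 18.5%.

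**Step 2: correlated outcomes.** For four equicorrelated standard normal statistics,

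risk(r) = 1 − ∫ φ(u) · [Φ((1.96 − √r·u)/√(1−r)) − Φ((−1.96 − √r·u)/√(1−r))]^4 du

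| Assumed r | Risk that at least one P<0.05 |
|---|---|
| 0 | 18.5% |
| 0.3 | 17.4% |
| 0.5 | 15.6% |
| 0.7 | 13.0% |
| 0.9 | 9.4% |
| 0.95 | 8.0% |
| 0.99 | 6.3% |

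Simulated t-tests with 30 per group (200,000 trials per value) gave 18.6%, 17.4%, 15.6%, 13.1% and 9.4% at r = 0, 0.3, 0.5, 0.7 and 0.9. With an assumed 24 per group the results were practically the same (17.5% at r = 0.3 and 9.5% at r = 0.9).

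**Step 3: other success rules.** If the CMS alone decides at one visit and side, the risk is 5%. If all four must be significant, it is at most 5%.

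**Step 4: separate tests by hand or visit.** The plan neither states nor excludes these. Testing rotation and grip in each hand would make six tests at a visit: 1 − 0.95^6 = 26.5% if independent, less if correlated. This shows direction only.

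**Step 5: what Holm would do.** Its first step uses 0.05/4 = 0.0125. With four independent tests the familywise risk is 1 − (1 − 0.0125)^4 = 4.9%, and it is at most 5% under any correlation.

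The cost in power, from the noncentral t distribution with 30 per group (58 degrees of freedom):
- Detectable difference at 80% power: 0.736 SD at alpha 0.05 and 0.886 SD at alpha 0.0125.
- Power for a 0.736 SD effect on the CMS: 80% at alpha 0.05 and 61% at alpha 0.0125.
- Full Holm procedure, simulated for correlations of 0.3 to 0.7: about 61% for the CMS if the other three outcomes have no effect, and about 70% if all four share the 0.736 SD effect.

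**The case against.** The strongest reply is that the CMS is already the primary in substance. Section 2.1 puts shoulder function first and section 2.2 ties its evaluation to the Constant score, so a sensible reader would judge the trial on that score and the error rate would be 5% at one visit and side. This has weight: it is the reason to choose the CMS in the fix. It does not settle the matter, because section 2.4 gives the other three the same primary label, and internal rotation is itself a measure of shoulder function, so section 2.1 does not single out the CMS.

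A second reply is that the any-one rule is the reviewer's assumption. That is correct. A reader might infer that the trial has a false-positive rate of 9% to 18.5%. The documents do not support that, because they adopt no success rule. What they show is that the rule is missing and that one permissible reading inflates the error.

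A third reply is that the outcomes are correlated. They may be, but the table covers this, and even at 0.9 the risk is nearly twice 5%.

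**Conclusion.** The concern holds in conditional form. The plan labels four outcomes primary, tests at an unadjusted 0.05, and states no hierarchy, primary visit or success rule. If any one of the four counts and there is no true effect, the risk at one visit with one test per outcome is 9.4% to 18.5% over assumed common correlations of 0.9 to 0.

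Two stronger readings should be resisted. The 9% end is not a floor: it comes from stopping at an assumed 0.9, and the value falls towards 5% as the correlation nears 1. Nor can the plan be charged with testing every outcome at every visit. Four outcomes at three follow-up visits would be 12 tests, or 1 − 0.95^12 = 46.0% if independent, but no such testing plan is stated. Separate tests by hand or visit would raise the risk above the one-visit figure; by how much cannot be fixed from the documents.

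This is a cheap improvement to the plan and does not invalidate the trial.

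**What to change.** **Preferred.** In sections 2.4 and 2.5, name one primary endpoint: the between-group difference in the 75-point adjusted CMS total at one stated visit from the month 6, 12 and 18 schedule in section 2.2. The 0, 8 and 12 month list in section 2.4 covers only the secondary outcomes and can be reconciled separately. If the CMS is scored per shoulder, which the documents do not say, name the side; section 2.3 admits only right-handed patients with a left fistula, so a named side is the same limb relative to the fistula in everyone. Make internal rotation, grip, biceps ultrasound and the other visits secondary, reported with confidence intervals.

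**Timing.** Fix the endpoint, visit, side and rule before any comparison by group. A choice made after group results are seen would bring back the selection problem. Section 4.1 requires ethics committee approval before the revision is implemented.

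**Cost.** No added patients or measurements. Three outcomes lose primary status.

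**Alternative.** Keep four primaries and state in section 2.5 that Holm applies across them at one named visit. Each outcome then needs one named variable and side, including the CMS side, the biceps side, and whether the biceps measure is area or thickness; otherwise there may be more than four tests. At Holm's strictest step, with 30 per group, the detectable difference at 80% power rises from 0.74 to 0.89 SD. Power for 0.74 SD on the CMS falls from 80% to about 61% if the other three have no effect, or to about 70% if all four share that effect.
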